6.2 Exploratory Endpoints

PIFR Endpoints:

1. Time to first occurrence of sPIFR (in days)
2. Number and proportion of sPIFR
3. Rate of sPIFR, defined as the number of sPIFR / number of days in the study, multiplied by 30 as sPIFR/month.

Exacerbation Endpoints:

Occurrence (yes/no), number, severity (mild, moderate, severe) and rate of COPD exacerbations over 24 weeks. Mild, moderate and severe exacerbations will be defined as:

1. Mild – doubling use of inhaled rescue medication > 48 hours and not meeting definition of moderate or severe
2. Moderate – increased rescue medication and either oral corticosteroid or antibiotics, not requiring hospitalization
3. Severe – hospitalization for exacerbation

6.3 Statistical Methods

Analysis populations

Full analysis set (FAS): all screened patients with informed consent and at least two consecutive PIFR measurements on different days.

Descriptive Statistics

Using the FAS, the following variables will be described using descriptive statistics (mean and standard deviation, min, max, median) and graphical displays (boxplots, histograms). Data transformation will be used if applicable, and extreme values will be verified and their effect on analysis results will be reported.

- demographics and clinical variables
- patient reported outcomes (CAT, mBORG and mMRC)
- concomitant diseases and medications

Primary analysis

The primary endpoint will be described as the proportion of patients with suboptimal PIFR and reported with 95% confidence intervals, on the FAS. The proportion of sPIFR will be computed from the Kaplan-Meier curve.

Subgroup analyses of the primary endpoint:

- per DPI device type (moderate vs. high resistance)
- per gender
- per GOLD stage based on spirometry results.

Analysis of exploratory endpoints: on FAS.

We will analyze the PIFR measurements over time, specifically:

- Descriptive analysis of PIFR measurements, including mean (SD), median (IQR), range over time per patient per device, and in different body positions (standing, sitting, supine at 45 degrees). PIFR curves per patient/device can be explored. Descriptive analysis for different time's period (week, month) may be explored.
- The time of first occurrence of sPIFR will be reported in days and will be plotted with a Kaplan-Meier curve. A patient will be considered censored for sPIFR at the time of the latest documented visit or PIFR measurements, the end of the study, the switching of device (between medium and high resistance DPI) or death (whichever occurs earlier), if they did not experience a sPIFR before. Associations with possible demographics and clinical variables will be explored using a Cox regression analysis.
- The proportion of suboptimal PIFR measurements will be reported with 95% CI, and also the rates. This analysis will also be performed per device in patients that used two devices with different resistances (e.g. Advair + Spiriva HH).
- We will explore, for each device, with logistic regression (binary) or negative binomial (count) the clinical and demographic factors associated with sPIFR measurements.
- We will use mixed models to explore associations of monthly PIFR averages over time and clinical and demographic factors. Subjects will be considered as random factor, other variables will be considered fixed effects.
- Association of PIFR with CAT score, mBORG score and mMRC
 - Association of PIFR and CAT scores at V1, V3, V4, V5, V6 (for PIFR, use the measurement in the week of each telephone follow-up, or the month average)

- Correlation of change in CAT scores with change in PIFR from baseline after 24 weeks
- Association of PIFR and mBORG score at V2, V3, V4, V5, V6
- Association of PIFR and mMRC scores at V1, V3, V4, V5, V6 (for PIFR, use the measurement in the week of each telephone follow-up, or the month average)

For COPD exacerbation analyses, the proportion of patients with COPD exacerbations (from Kaplan Meier curve) and the rate of exacerbations occurring during follow-up will be reported along with 95% CI. A patient will be considered censored for exacerbations at the time of the last documented visit, the end of the study, the switching of device (between medium and high resistance DPI) or death (whichever occurs earlier), if they did not experience an exacerbation before. The exacerbations will be reported overall and stratified by severity. The associations between exacerbations and PIFR will be explored in different ways, for all exacerbation, stratified by severity of exacerbations, and stratified by device.

- The rate of exacerbations and sPIFR will be analyzed with negative binomial models (or another model if more appropriate).
- For patients with exacerbations, the mean of PIFR in the week before, of, and after each exacerbation will be calculated and reported.

All tests with p value < 0.05 will be interpreted nominally as statistically significant.

Missing data

- No imputation for PIFR
- No imputation for COPD exacerbations
- No imputation for CAT, mBORG and mMRC

Sample Size and Power

In this application, we propose to recruit 120 COPD participants for study enrollment. There are several rationales for this sample size selection.

The primary outcome focuses on characterizing the proportion of participants with suboptimal PIFR. There are no available data on prevalence of sPIFR from home measurements in COPD, highlighting the novelty of this proposal. While there is no established clinical threshold of variability of proportion with suboptimal PIFR, it is felt that a precision of <10% (95% CI range <20%) is desirable for clinical interpretation of sPIFR prevalence. From pilot study data, we observed that 40% of patients had sPIFR. We have generated three scenarios with different ranges of proportion of sPIFR (30%, 40%, and 50%) along with the required sample sizes to obtain a range of precisions (see table). Given that clinical expertise and judgement suggests that a precision of <10% is acceptable for this study, one can see that sample size range of N=105 to 125 will achieve this precision across a range of possible sPIFR proportions (highlighted column).

sPIFR proportion	Precision (half of Confidence Interval)				
	5%	8.8%	10%	15%	20%
30%	323	105	81	36	21
40%	369	120	93	41	24
50%	385	125	97	43	25

Interim Analysis

None planned

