3.4 Study Population

Our study population will be outpatients with moderate, severe, or very severe COPD.

Participants will be recruited from multiple sources as described above.

Inclusion Criteria:

- Age > 50 years-old
- Spirometry-confirmed diagnosis of COPD (FEV1/FVC <0.70)
- GOLD II-IV based on existing spirometry results
- CAT score > 10
- For high resistance DPI, baseline PIFR < 90 L/min (InCheck DIAL®) and >=30 L/min; for medium resistance DPI, PIFR ≤ 90 L/min (InCheck DIAL®) and >=60 L/min. Handihaler is a high resistance DPI. Examples of medium resistance DPI: Anoro, Incruse, Breo Ellipta®, Advair® Diskus®, or Wixela® Inhub® DPI
- History of smoking tobacco products > 10 pack years
- Prescribed at least one daily maintenance DPI with no change in prescription within the four weeks prior to the Enrollment Visit
- One or more exacerbations of COPD requiring systemic corticosteroids within last 3 years
- Patients will be enrolled with regards to the below pre-specified characteristics based on gender and the prescribed maintenance inhaler(s) as follows (note that patients are commonly prescribed multiple inhalers):
 - Male : Female ratio 1:1 (+ 10%)
 - Target recruitment stratified to two treatment arms:

- N=60 patients receiving medium resistance DPI (Anoro, Incruse, Breo Ellipta®, Advair® Diskus®, or Wixela® Inhub® DPI) with planned recruitment to include 50% of participants on Diskus® and 50% on Ellipta®
- N= 60 patients receiving high resistance DPI (Spiriva Handihaler® DPI)

For all study participants, participants may also receive another MDI, Respimat® inhaler, or DPI (e.g. Breo Ellipta® + Spiriva Respimat®, Symbicort MDI® + Spiriva Handihaler®, Advair Diskus® + Spiriva Handihaler®, Wixela® Inhub® + Spiriva Handihaler®) Subjects will be placed into one of the two cohorts based on the DPI, if on more than one DPI, they will be placed into the cohort for the DPI with the highest resistance (Handihaler>Ellipta=Diskus=Inhub). These strata are for recruitment only, and PIFR measurement for both DPIs will be recorded and used in analyses.

Exclusion Criteria:

- Inability to demonstrate proper technique for the InCheck DIAL® device
- Inability to achieve minimum PIFR for prescribed DPI(s) at screening/enrollment visit (< 30 L/min for e.g., Handihaler® (High resistance DPI), < 60 L/min for Ellipta® (Medium resistance DPI))
- Neuromuscular disease associated with weakness

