4 STUDY PROCEDURES

4.1 Home Monitoring

Subjects will record their PIFR using the InCheck DIAL® and modified Borg dyspnea score three times weekly (MWF) when clinically stable and daily while respiratory symptoms worsen per patient self-assessment. At each session, the participant will repeat efforts three times, with the highest of the three repeated efforts being recorded by the participant. They will be asked to perform the PIFR for the DPI(s) they are receiving at home (Ellipta®, Inhub®, Diskus® or Handihaler®) using the InCheck DIAL®. If on more than one DPI, patient will record PIFR for each device. PIFR will be recorded with best approximation to nearest 1 L/min.

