6 STATISTICAL CONSIDERATION

6.1 Primary Endpoint

For each patient the occurrence of suboptimal Peak Inspiratory Flow Rate (sPIFR) over 24 weeks. sPIFR will be defined as any two consecutive measurements on different days below the optimal threshold for any prescribed DPI (e.g., <30 L/min for Handihaler® (High resistance DPI), <60 L/min for Ellipta® (Medium resistance DPI))

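### The device-type subgroup of the primary endpoint does not say which device's readings count or where patients on both device types belong

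*Combined protocol and SAP*

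**What the plan says.** Section 6.1 makes the primary endpoint a patient-level event, met by "any two consecutive measurements on different days below the optimal threshold for any prescribed DPI". The thresholds are 30 L/min for high and 60 L/min for medium resistance. Section 6.3 estimates the proportion of patients with the event from the Kaplan-Meier curve, with a 95% confidence interval. It then lists subgroup analyses of that same endpoint, the first being "per DPI device type (moderate vs. high resistance". (I take moderate here to be the class called medium elsewhere.) It gives no event specific to a device type and does not say which subgroup a patient on both types belongs to.

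Dual use is expected. Section 3.4 and the Synopsis give Handihaler combined with Diskus or Inhub as examples. For these patients Section 3.4 says "if on more than one DPI, they will be placed into the cohort for the DPI with the highest resistance", and the next sentence limits that rule: "These strata are for recruitment only, and PIFR measurement for both DPIs will be recorded and used in analyses". Section 4.1 secures the data: "If on more than one DPI, patient will record PIFR for each device".

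Device-level results also appear among the exploratory analyses in Section 6.3. The proportion and rates of suboptimal measurements come with the note "This analysis will also be performed per device in patients that used two devices with different resistances", and logistic or negative binomial models are planned for each device.

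**The concern.** A subgroup labelled by device type will be read as a result for that device type. With an any-DPI event it need not be one. A patient on Handihaler and Diskus who falls below 60 L/min only at the Diskus setting has had the primary event, and could be shown under high resistance although every Handihaler reading was adequate.

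This matters because device is a named predictor in the objectives (Section 2.1) and recruitment is built as 60 and 60 on resistance class. Leaving the handling of dual users open also allows it to be settled after the data have been seen, in a study without blinding.

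**Working it through.** **1. The plan's own figure.** The sample-size table follows n = 1.96² × p(1−p) / d², rounded up. For p = 0.40 and d = 0.088: 3.8415 × 0.24 / 0.007744 = 119.05, so 120, as printed. All 15 cells reproduce. None depends on the device-type subgroup, so nothing below changes N.

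**2. Where dual users could go, keeping the any-DPI event.**

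| Handling | Consequence |
|---|---|
| High-resistance group (recruitment rule reused) | Medium-setting events count as high-resistance events |
| Both groups | The same, and Handihaler events also count in the medium group |
| Third group, or excluded | The two single-type groups are clean |

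Section 6.3 states none of these.

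**3. Direction.** In any one patient, a Handihaler event is also an any-DPI event. The underlying any-DPI proportion therefore cannot be below the Handihaler proportion in the same patients. It is strictly higher as soon as some dual user has the event on the medium device alone.

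**4. Size, under assumptions.** Let pH and pM be the 24-week event proportions on each device, taken as equal in single and dual users, and let f be the dual share of the high-resistance group. Then

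high-group proportion = (1−f) × pH + f × p_any,

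where p_any runs from max(pH, pM) (full overlap) to 1 − (1−pH)(1−pM) (independence).

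For pH = 20% and pM = 40%, p_any runs from 40% to 1 − 0.8 × 0.6 = 52%.
- f = 20%: 0.8 × 0.20 + 0.2 × 0.40 = 24.0%, up to 0.8 × 0.20 + 0.2 × 0.52 = 26.4%.
- f = 50%: 0.5 × 0.20 + 0.5 × 0.40 = 30.0%, up to 0.5 × 0.20 + 0.5 × 0.52 = 36.0%.

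| Assumed pH / pM | f = 20% | f = 36% | f = 50% | f = 87.5% |
|---|---|---|---|---|
| 20% / 40% | 24.0-26.4% | 27.2-31.5% | 30.0-36.0% | 37.5-48.0% |
| 27% / 47% | 31.0-33.9% | 34.2-39.3% | 37.0-44.2% | 44.5-57.0% |
| 40% / 40% | 40.0-44.8% | 40.0-48.6% | 40.0-52.0% | 40.0-61.0% |

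The device-specific value in each row is pH.

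Where the inputs come from:
- 27% and 47% are normal approximations to the pilot data in Section 1.3: Φ((30−36)/10) = 0.27 and Φ((60−61)/13) = 0.47. They describe single readings in patients who could already be below threshold, whom this study excludes, so they are illustrative only.
- The dual share is not known. The pilot counts (11, 25 and 14) sum to 50 for 27 patients. Taken as printed, 14/(25+14) = 36%. If the 25 had to be 27 − 11 − 14 = 2, the share would be 14/16 = 87.5%. The values 20% and 50% are plain assumptions.

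**5. If dual users enter both groups.** With g the dual share of the medium group, that group becomes (1−g) × pM + g × p_any. At 20%/40% and g = 50%: 0.5 × 0.40 + 0.5 × (0.40 to 0.52) = 40-46%, against 40%.

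**6. The gap between devices** (dual users in the high group only, f = 20-50%). At 20%/40% the device-specific gap of 20 points becomes 40 − 36 = 4 to 40 − 24 = 16 points. At 40%/40% there is no true gap, and one of up to 52 − 40 = 12 points appears in the other direction.

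**7. Against sampling error.** With 60 patients and p = 40%, the 95% half-width is 1.96 × √(0.24/60) = 12.4 points. For a difference between two such groups it is 1.96 × √(2 × 0.24/60) = 17.5 points.

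**The case against.** The strongest reply is that the plan does not make the mistake; it only leaves the point unstated. The sentence after the placement rule confines that rule to recruitment. Thresholds are set per resistance class and readings are taken per device, so the subgroup line could be meant as each device's readings against its own threshold. That much stands: this is an unspecified analysis, not one shown to be wrong.

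Second, the subgroup is not the only device-level result. The exploratory rate is built on sPIFR, which Section 6.1 defines as the two-reading event. The per-device rates in dual users can therefore be read as device-specific event rates, and per-device regressions are planned too. This also stands, but neither gives the Kaplan-Meier proportion of patients by device, which is what the subgroup reports.

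Third, the consequence is limited. The primary analysis is descriptive, the Synopsis says the study is not powered to test inhalers against each other, and the interval for a difference is wider than most of the shifts above. That bears on importance, but sampling error does not excuse a proportion that may not match its label.

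Fourth, letting dual users count under both devices makes the groups overlap. This is correct, and the fix has to deal with it.

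**Conclusion.** The gap is real and worth closing. The device-type subgroup rests on an any-DPI event, with no statement of whose readings count or where dual users belong. Under two of the natural ways of filling that gap, the high-resistance proportion is at least as high as its device-specific value, and probably higher. On the assumptions of 20% and 40% event rates and a dual share of 20-50%, it would read about 24-36% instead of 20%. These inputs are assumed, as is equality of device-specific rates in single and dual users; the documents do not supply them reliably.

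Three stronger readings are tempting and not supported:
- That the plan assigns dual users to the high-resistance group for analysis. Section 3.4 says those strata serve recruitment only.
- That a difference between device types would necessarily be hidden. It shrinks when the medium device has the clearly higher event rate, but with equal rates a spurious difference in the other direction can appear.
- That the primary result is affected. The overall any-DPI estimate and N=120 are unchanged.

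**What to change.** In Section 6.3, for the device-type subgroup only:
- Define sPIFR by setting: two successive readings, taken on different days, under 30 L/min at the high-resistance setting, or under 60 L/min at the medium-resistance setting.
- Estimate the 24-week Kaplan-Meier proportion for each device type among all patients prescribed it, with dual users contributing to each estimate.
- State that any between-device comparison allows for within-patient correlation, for example by a bootstrap that resamples patients.
- Alternatively, show three groups: medium only, high only, and both.

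Keep the any-DPI event for the overall estimate, and fix the choice before the data are examined.

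The cost is a few sentences of text and a small amount of programming. No new data are needed, because home readings are already recorded per device, and the sample size does not change. The one drawback is that the two device groups overlap and are not independent. The bootstrap deals with this for comparisons, and the three-group display avoids it.

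### Both Kaplan-Meier analyses censor at death, so the 24-week proportions can be slightly off, and a fatal exacerbation may be missed or graded below severe

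*Combined protocol and SAP*

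**What the plan says.** Section 6.1 defines the primary endpoint per patient: "For each patient the occurrence of suboptimal Peak Inspiratory Flow Rate (sPIFR) over 24 weeks". Section 6.3 describes it as a proportion of patients with a 95% confidence interval, and then adds: "The proportion of sPIFR will be computed from the Kaplan-Meier curve". The only censoring rule for that curve is in the paragraph on time to first sPIFR. It takes the earliest of the latest visit or PIFR measurement, the end of the study, a switch between resistance classes, "or death (whichever occurs earlier), if they did not experience a sPIFR before".

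For exacerbations, section 6.3 reports "the proportion of patients with COPD exacerbations (from Kaplan Meier curve", with a parallel rule: "A patient will be considered censored for exacerbations at the time of the last documented visit", or at the end of the study, at a device switch, "or death (whichever occurs earlier), if they did not experience an exacerbation before". Neither analysis has a competing-risk estimator, a composite with death, or a sensitivity analysis for deaths.

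The severity classes are in section 6.2, the synopsis and the Appendix 1 footnote:

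- **Mild:** "doubling use of inhaled rescue medication > 48 hours and not meeting definition of moderate or severe" (the synopsis and Appendix 1 put the limit at 48 hours or more).
- **Moderate:** increased rescue use plus an oral corticosteroid or antibiotic, without admission (Appendix 1 names the corticosteroid only).
- **Severe:** "Severe – hospitalization for exacerbation".

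No class mentions death.

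Under section 4.2, exacerbations are ascertained by telephone at weeks 4, 8, 12 and 24. Section 4.3 allows no unscheduled visits.

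**The concern.** Censoring a death treats the patient as someone who could still have had the event later, at the rate of those who remain. One minus Kaplan-Meier then estimates the risk in a setting where nobody dies. That is not the proportion of enrolled patients who have the event within 24 weeks, which is what section 6.1 defines and what the sample-size section is built on. One minus Kaplan-Meier is never below the cumulative incidence, so for sPIFR any error goes upward.

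For exacerbations there is a second problem. Death in COPD can be the outcome of an exacerbation, so it is not independent of the event. Severe is defined by admission alone, so a patient who dies of an exacerbation outside hospital cannot be graded severe. If no rescue-use or treatment criterion is documented either, the patient is censored as exacerbation-free. The ascertainment makes this easier to miss, because a patient who has died cannot answer the next call.

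The censoring date adds to this. The earliest date applies, so a patient who dies in week 20 after a call at week 12 is censored at week 12. An admission between those dates, or the death itself, then falls outside the analysed follow-up.

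**Working it through.** **1. The plan's own figure.** The sample-size table uses n = 1.96² × p(1−p)/d², rounded up. At d = 8.8%, p = 30%, 40% and 50% give 104.17, 119.05 and 124.01, so 105, 120 and 125 as stated. All 15 cells of the table reproduce. With N = 120 the half-width is 8.2, 8.8 and 8.9 points. This is the precision of a simple proportion of patients.

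**2. Size of the sPIFR overstatement.** The documents give no mortality, so 24-week mortality q of 1-5% is an assumption, with 10% as an extreme. The sPIFR levels p = 30%, 40% and 50% are the plan's scenarios, taken as the value of one minus Kaplan-Meier. With constant hazards λ = −ln(1−p)/24 and μ = −ln(1−q)/24 per week:

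cumulative incidence = λ/(λ+μ) × [1 − (1−p)(1−q)].

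For p = 40% and q = 3%: 24λ = 0.5108 and 24μ = 0.0305, so the ratio is 0.9437. The bracket is 1 − 0.60 × 0.97 = 0.418. The product is 39.45%, against 40.0% from one minus Kaplan-Meier, a gap of 0.55 points.

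Overstatement in percentage points:

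| 1 − KM | q = 1% | q = 2% | q = 3% | q = 5% | q = 10% |
|---|---|---|---|---|---|
| 30% | 0.14 | 0.28 | 0.43 | 0.71 | 1.44 |
| 40% | 0.18 | 0.37 | 0.55 | 0.92 | 1.87 |
| 50% | 0.22 | 0.44 | 0.67 | 1.12 | 2.26 |

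**3. The same effect in whole patients.** Take 120 patients with 48 sPIFR events spread evenly over 168 days, so the observed proportion is 48/120 = 40.0%. By day 84, 24 events have occurred and 96 patients remain at risk. If k event-free patients die on day 84 and are censored:

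1 − KM = 1 − (96/120) × (96−k−24)/(96−k).

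This gives 40.0% for k = 0, 40.4% for k = 2, 40.9% for k = 4 and 41.3% for k = 6.

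**4. Exacerbations: the direction depends on cause of death.** Use the same layout, with 48 patients having a recorded exacerbation and two further patients dying on day 84 without one. The planned analysis gives 40.4% whatever the cause.

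- If both deaths are unrelated to exacerbation, the observed proportion is 48/120 = 40.0%, so the plan is 0.4 points too high.
- If both are fatal exacerbations that met no class, it is 50/120 = 41.7%, so the plan is about 1.2 points too low.

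With three such fatal exacerbations the figures are 51/120 = 42.5% and 1 − 0.8 × 69/93 = 40.65%. The numbers of deaths and exacerbations here are illustrative, since the documents give neither rate. For the severe class alone, two uncounted deaths are 2/120 = 1.7 points.

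**5. Where a fatal exacerbation without admission goes.** Mild and moderate do not require survival. A patient whose rescue use met the mild criterion is counted as mild. One with increased rescue use and a qualifying treatment is counted as moderate. Only a patient with none of these documented is lost. None can be graded severe.

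**The case against.** The primary analysis is descriptive, with no hypothesis test or decision threshold. A shift of about one point at most, under an assumed mortality, changes no conclusion against a half-width of 8.2 to 8.9 points. With no event-free deaths the shift is zero. That stands, and it limits the importance of the point.

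One minus Kaplan-Meier can also be defended as the risk of sPIFR among patients who stay alive and observed, and it handles dropout. The second part is true, but cumulative incidence handles dropout equally well. The first describes a different quantity from the one in section 6.1.

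A reader might infer that a fatal exacerbation outside hospital fits no severity class. The definitions do not support that, because such a patient can qualify as mild or moderate and would then be under-graded, not lost. A reader might also infer that the exacerbation proportion is biased in a known direction. It is not, because the two effects oppose each other. Nor can it be said that severe results will rest on few events, since the documents give no exacerbation or admission rate.

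Finally, adding death as a competing event is not enough by itself. While the earliest-date wording remains, a death after the last contact still falls after the censoring date. The fix has to cover this.

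**Conclusion.** The point holds as a minor one. Both analyses censor at death although the target is a proportion of patients over 24 weeks. For sPIFR the result is an overstatement of about 0.1 to 1.1 points, given constant hazards, sPIFR of 30-50% and an assumed 24-week mortality of 1-5%. The tempting stronger reading, that the primary proportion is overstated as a matter of course or that the primary result is in doubt, is not supported: the effect needs deaths before sPIFR, and it is small beside the planned precision.

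For exacerbations the net direction is undetermined. What is established from the text is a gap in definition and dating. A fatal exacerbation without admission is never severe and may not be counted at all, and an event between the last call and death, even one with admission, may fall after censoring. How often this would happen cannot be judged from the documents.

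**What to change.** In section 6.3:

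- Estimate the sPIFR and exacerbation proportions by cumulative incidence (Aalen-Johansen), with death as a competing event on its actual date.
- Amend the earliest-date wording in both rules so that a known death is not replaced by an earlier last-visit or last-measurement date.
- Leave censoring for end of study, loss to follow-up and device switch as it is.
- Report the number of deaths.

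In section 6.2, the synopsis and Appendix 1, count death due to exacerbation as a severe event for the analysis, dated at death. Take the cause from the adverse event records kept under section 10.2 or from the medical record, and check the same records for an exacerbation between the last contact and death.

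The cost is small: a change of wording, a standard software option, and the date and cause of death from existing records. That last item is some work, because deaths are not on the chart-abstraction list in section 5.1.1, telephone interviews cannot supply them, and the fatal-event reporting in section 10.3 covers only events associated with the listed drugs. Settling the rule before the data are seen avoids deciding afterwards how to count a particular death.

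### The logistic and negative binomial predictor models for sPIFR are planned only per device, with no pooled model and no factor-by-device test, so power is low and a common effect may be misread as device-specific

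*Combined protocol and SAP*

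**What the plan says.** Section 2.1 makes associations between PIFR and potential predictors, device among them, an exploratory objective. Three analyses in section 6.3 serve it:

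- **Logistic or negative binomial models, split by device:** "We will explore, for each device, with logistic regression (binary) or negative binomial (count) the clinical and demographic factors associated with sPIFR measurements". No covariate list, limit on covariates, pooled version or interaction with device is given.
- **A Cox regression** of time to first sPIFR on demographic and clinical variables, with no split by device and no device term named.
- **A mixed model** of monthly PIFR averages with a random subject effect, also unsplit and without a named device term.

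The reading rule for all tests is: "All tests with p value < 0.05 will be interpreted nominally as statistically significant".

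Section 3.4 recruits two cohorts: "N= 60 patients receiving high resistance DPI (Spiriva Handihaler® DPI") and "N=60 patients receiving medium resistance DPI (Anoro, Incruse, Breo Ellipta®, Advair® Diskus®, or Wixela® Inhub® DPI"). A patient on more than one DPI is placed in the cohort of the highest resistance, but the cohorts serve recruitment only, and PIFR for both DPIs is analysed. The sample size in section 6.3 rests on the precision of one overall proportion. It contains no power calculation for any predictor.

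**The concern.** Splitting these models by device halves the cohort, or nearly so, for every factor studied. Nothing in the sample size section shows that the halves are large enough. A split also provides no comparison between devices. If a factor has p<0.05 in one class and p>0.05 in the other, nothing in the plan distinguishes a real difference from the chance result expected when power is moderate in both. At stake is the predictor objective: factors that act in both classes are likely to be missed in these models, and a chance pattern may be reported as a device effect.

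**Working it through.** **The plan's own figure.** The sample size table follows n = 1.96² × p(1−p) / d². At p = 0.40 and d = 0.088 this is 3.8416 × 0.24 / 0.007744 = 119.05, rounded up to 120. All 15 cells reproduce. The table therefore concerns one proportion in all 120 patients and does not bear on the predictor models.

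**Patients with sPIFR per model.** Inputs are 60 patients per class (section 3.4) and 30%, 40% or 50% sPIFR (section 6.3).

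| Model | Patients | 30% | 40% | 50% |
|---|---|---|---|---|
| One class | 60 | 18 | 24 | 30 |
| All patients | 120 | 36 | 48 | 60 |

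At the usual 10 events per parameter, a class model supports 1.8 to 3 parameters and a pooled model 3.6 to 6.

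**Why 18-30 is not a bound.** A Handihaler patient who also uses a medium DPI enters both models.
- If 25% do so (assumed), the medium class has 60 + 0.25 × 60 = 75 patients and 23 to 38 with sPIFR.
- If 52% do so (14 of 27 in the pilot as printed, although the pilot's counts 11 + 25 + 14 = 50 do not fit 27), it has about 91 patients and 27 to 46 with sPIFR.
- In the other direction, section 3.4 excludes patients below threshold at entry, so home sPIFR could fall below the planning range. At an assumed 20%, 60 patients give 12.

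**Power for an effect common to both classes.** Assumptions not in the documents: continuous factor, odds ratio 1.7 per SD in both classes, 40% sPIFR, two-sided 5% test, no dropout.
- Approximation: SE of the log odds ratio = 1/√(n × 0.24), and ln 1.7 = 0.531.
- n = 60: SE 0.264, z = 2.01, power Φ(2.01 − 1.96) ≈ 52%.
- n = 120: SE 0.186, z = 2.85, power Φ(2.85 − 1.96) ≈ 81%.
- Simulated logistic models run a little lower, as expected in small samples: 42-46% per class and 77% pooled.

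**Discordance between classes.** With power P in each of two independent classes, the chance of significance in exactly one is 2P(1−P). At P = 0.45 this is 2 × 0.45 × 0.55 = 0.495; simulation gave 49%. When the effect was truly the same, an interaction test was falsely significant in about 3% of studies.

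**A different effect type.** For a binary factor split 50:50 at 40% sPIFR:

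| Odds ratio | Power, n = 60 | Power, n = 120 | Significant in exactly one class |
|---|---|---|---|
| 2 | 25% | 45% | 38% |
| 2.5 | 40% | 68% | 48% |
| 3 | 53% | 83% | 50% |

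The pattern does not depend on the first choice of effect.

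**The case against.** - **Other predictor analyses are unsplit.** This stands in part. The Cox model has 36 to 60 first events and 55% to 77% power for an assumed hazard ratio of 2. The mixed model uses the continuous measure, usually more informative than a dichotomy. It would be wrong to infer that every predictor analysis is split, or that real predictors will necessarily be missed. However, the Cox model stops at the first sPIFR, the mixed model concerns mean PIFR, and neither covers the sPIFR count or names a device term.
- **Separate models are defensible.** Thresholds are 30 and 60 L/min for the two classes, and eligibility windows differ, so the outcome is not identical. This stands, and is why the per-device estimates should stay.
- **An interaction test would be weak.** This also stands. Its SE is √2 × 0.264 = 0.373, so 80% power needs a ratio of odds ratios of exp(2.8 × 0.373) ≈ 2.8, and power at a ratio of 1.7 is about 30%. Its main use is to guard against claiming a difference that the data do not show.
- **The count model carries more information.** Repeated home measurements add to an any/none outcome, so the power figures apply to the logistic model only. The number of independent patients still limits both.
- **A smaller sample per model might be inferred.** Because recruitment specifies "planned recruitment to include 50% of participants on Diskus® and 50% on Ellipta", a reader might take device as individual product and arrive at 30 patients and 9 to 15 with sPIFR. Section 6.3 does not support that: its subgroups, its censoring rule and its dual-use analysis all describe devices by resistance, and section 3.4 reserves the strata for recruitment.
- **No misreading is planned.** A reader might infer that one-sided results will be reported as device-specific. No section says so; p-values are nominal and the work is exploratory. It is a risk only.

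**Conclusion.** The concern holds for the logistic and negative binomial models. By resistance class they have about 60 patients each and 18 to 30 with sPIFR at the planning proportions, with more possible in the medium class through dual users and fewer in either if sPIFR is rarer than assumed. For a common odds ratio of 1.7 per SD at 40% sPIFR, splitting lowers power from about 77% to about 45%, and about half of studies would show nominal significance in one class only. These figures rest on the assumed effect size, no dropout and independent classes. Dual users break the last assumption, and the plan does not address it. The consequence is confined to an exploratory objective; the primary proportion and its interval are unaffected. This is a worthwhile improvement rather than a necessary correction.

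**What to change.** In section 6.3:

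1. State that device means resistance class in these models, if that is the intent.
2. Keep the per-device estimates and add one logistic and one negative binomial model over all patients, with resistance class as a covariate.
3. Let a dual user contribute one record per DPI, with standard errors clustered on patient.
4. Pre-specify a factor-by-class interaction test, and claim a device-specific effect only from that test, not from significance in one class and its absence in the other.
5. List the candidate factors and limit their number to what the events support, or use Firth penalisation for the logistic model where events are sparse.

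The cost is SAP wording and some additional analysis, with no new data or patients. The downside is that the pooled main effects assume factors act similarly in both classes, and the interaction test can rule out only large differences.
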